7.3.3.3 Dose Modification Criteria for FOLFOX

Recommended dose modifications of FOLFOX are provided in Table 7.3.3.3-1 and criteria for dose modification of FOLFOX are provided in [Table 7.3.3.3-2](#).

Table 7.3.3.3-1: Recommended Dose Modifications of FOLFOX

Drug	Starting Dose	Dose Modification	
		Dose Level - 1	Dose Level - 2
Oxaliplatin	85 mg/m ²	70 mg/m ²	50 mg/m ²
5-FU	Bolus 5-FU: 400 mg/m ² Leucovorin: 400 mg/m ² Infusion 5-FU: 2400 mg/m ² /48 hours	Bolus 5-FU: 300 mg/m ² Leucovorin: 300 mg/m ² Infusion 5-FU: 2000 mg/m ² /48 hours	Bolus 5-FU: 200 mg/m ² Leucovorin: 200 mg/m ² Infusion 5-FU: 1600 mg/m ² /48 hours

Abbreviation: 5-FU: 5-fluorouracil.

Table 7.3.3.3-2: Criteria for Dose Modifications of FOLFOX

Toxicity	Definition	During a course of therapy	Dose adjustments for next treatments
Neutropenia	Grade 3 or greater	Interrupt until resolved to Grade 2	Dose level -1 *If treatment delayed for 4 consecutive weeks, discontinue all treatment
Thrombocytopenia	Grade 2	Interrupt until resolved to Grade 1	Dose level -1 *If Grade 2 persists > 7 days, oxaliplatin reduced by 2 dose levels when platelets improve to Grade 1
	Grade 3	Interrupt until resolved to Grade 1	Dose level -1 *If Grade 3 persists > 7 days, oxaliplatin reduced by 2 dose levels when platelets improve to Grade 1
	Grade 4	Interrupt until resolved to Grade 1	Dose level -1 *If Grade 4 persists > 7 days, oxaliplatin reduced by 2 dose levels when platelets improve to Grade 1
Neurologic toxicity	Grade 2 peripheral sensory neuropathy	Interrupt until resolved to Grade 1	Oxaliplatin dose -1 Continue 5-FU and leucovorin *If oxaliplatin delayed for neurologic toxicity for 4 consecutive weeks, discontinue oxaliplatin, continue 5-FU and leucovorin
	Grade 3 or greater peripheral sensory neuropathy	Discontinue oxaliplatin	Continue 5-FU and leucovorin
Gastrointestinal toxicities	Grade 2 or greater diarrhea	Interrupt until resolved to Grade 1	Dose level -1 If dose delayed for diarrhea for 4 consecutive weeks, discontinue all treatment

For toxicities not listed above, dose modifications are permitted per local standards. Participants may also discontinue oxaliplatin following multiple cycles if, in the investigator’s judgment, cumulative toxicity is likely to increase over time and become problematic.

7.3.3.4 Dose Modification Criteria for SOX Including Initiation and Continuation

The dosage and the necessity of treatment interruption should be checked for each participant before the start of each administration in accordance with the following criteria for starting treatment. Decisions on dose interruption and dose reduction should be made on the basis of the latest data available at the time.

Criteria for Starting SOX Therapy

Prior to starting SOX therapy, it must be confirmed whether the participant fulfills the criteria in Table 7.3.3.4-1. If the participant does not meet all of the criteria, the study treatment could be postponed until all of the criteria are met. Note that, even if a participant does not meet 1 or more of the following criteria, SOX therapy may be administered if treatment is expected to lead to clinical benefit, SOX therapy is not contraindicated and can be safely administered to the participant. If any of the criteria for starting SOX therapy are not met at subsequent doses, the dose should be reduced by 1 level, and the acceptability of the administration and the need for postponement will be determined according to the criteria for starting treatment at postreduction doses.

Table 7.3.3.4-1: Criteria for Starting SOX Therapy

Parameter	Criteria
White blood cells	$\geq 3000/\text{mm}^3$ (only for dose of $130 \text{ mg}/\text{m}^2$ oxaliplatin)
Neutrophils	$\geq 1500/\text{mm}^3$
Platelets	$\geq 100000/\text{mm}^3$ (only for dose of $130 \text{ mg}/\text{m}^2$ oxaliplatin) $\geq 75000/\text{mm}^3$
AST/ALT	$\leq \text{ULN} \times 2.5$ (or $\leq \text{ULN} \times 5.0$ in the presence of liver metastasis)
Serum creatinine	$\leq \text{ULN} \times 1.2$
Infection	No fever $\geq 38^\circ\text{C}$ suggesting infection
Diarrhea, stomatitis, Hand-Foot syndrome	Grade ≤ 1

Abbreviations: ALT = alanine aminotransferase; AST = aspartate aminotransferase; ULN = upper limit of normal.

Criteria for Interruption of SOX Therapy

If any of the criteria in Table 7.3.3.4-2 are met after starting tegafur-gimeracil-oteracil, tegafur-gimeracil-oteracil potassium should be interrupted then resumed after the criteria are met. Doses of tegafur-gimeracil-oteracil potassium omitted for toxicity are not replaced.

Table 7.3.3.4-2: Criteria of Interruption of Tegafur-Gimeracil-Oteracil Potassium

Parameter	Criteria of Interruption of Tegafur-Gimeracil-Oteracil Potassium (Within the Same Treatment Period)
Neutrophils	$< 1000/\text{mm}^3$ (Grade ≥ 3)
Platelets	$< 50000/\text{mm}^3$ (Grade ≥ 3)
AST/ALT	$> \text{ULN} \times 2.5$ (or $> \text{ULN} \times 5.0$ in the presence of liver metastasis)
Serum creatinine	$> \text{ULN} \times 1.2$
Infection	Fever $\geq 38^\circ\text{C}$ suggesting infection

Table 7.3.3.4-2: Criteria of Interruption of Tegafur-Gimeracil-Oteracil Potassium

Parameter	Criteria of Interruption of Tegafur-Gimeracil-Oteracil Potassium (Within the Same Treatment Period)
Diarrhea, stomatitis, Hand-Foot syndrome	Grade \geq 2

Abbreviations: ALT = alanine aminotransferase; AST = aspartate aminotransferase; ULN = upper limit of normal.

Criteria for Dose Reduction of SOX Therapy

On the planned day of administering SOX therapy, it must be confirmed whether the participant fulfills the criteria in Table 7.3.3.4-3. If the participant meets any of the criteria at any time during the last dose and start of subsequent dose, 1 or both agents must be reduced according to Table 7.3.3.4-4 and be continued. Once the dose has been reduced, it should not be increased at a later time.

Table 7.3.3.4-3: Criteria for Dose Reduction of SOX Therapy

Adverse Events		Next Doses	
Parameter	Criteria	Oxaliplatin	Tegafur-Gimeracil-Oteracil Potassium
Decreased platelet count	(only for dose of 130 mg/m ² oxaliplatin) Not met \geq 100000/mm ³ within 7 days of planned date of dosing	1-level reduction	-
	Not met \geq 75000/mm ³ (Grade \leq 1) within 7 days of planned date of dosing		
	(only for dose of 50 mg/m ² oxaliplatin) Not met \geq 75000/mm ³ (Grade \leq 1) within 7 days of planned date of dosing	-	1-level reduction
	< 25000/mm ³ (Grade 4)	1-level reduction	1-level reduction
Decreased neutrophil count	< 500/mm ³ (Grade 4)	1-level reduction	1-level reduction
Febrile neutropenia	Neutrophil count < 1000/mm ³ with fever \geq 38°C (axillary temperature)	1-level reduction	1-level reduction
Diarrhea, stomatitis, Hand-Foot syndrome	Grade \geq 3	1-level reduction	1-level reduction
Allergic reaction/hypersensitivity suspected to be due to	Grade \geq 3	Discontinued	-

Table 7.3.3.4-3: Criteria for Dose Reduction of SOX Therapy

Adverse Events		Next Doses	
Parameter	Criteria	Oxaliplatin	Tegafur-Gimeracil-Oteracil Potassium
administration of oxaliplatin			
Peripheral neuropathy	Grade 2	1-level reduction	-
	Grade 3	Skip dosing ^a	-
	Grade 4	Discontinued	-

^a Resume dosing from 1-level reduction after recovering Grade 2 or less.

Table 7.3.3.4-4: Doses of SOX Therapy for Dose Reduction

Dose Reduction Level	Oxaliplatin (mg/m ²)	Tegafur-Gimeracil-Oteracil Potassium (mg/dose)		
		< 1.25 m ²	≥ 1.25 m ² to < 1.5 m ²	≥ 1.5 m ²
Initial dose	130	40	50	60
1-level reduction	100	25	40	50
2-level reduction	75	20	25	40
3-level reduction	50	Discontinued ^a		
4-level reduction	Discontinued	-		

^a If tegafur-gimeracil-oteracil potassium combination drug is discontinued, oxaliplatin should also be discontinued.

7.3.4 Criteria for Oxaliplatin-Plus-Fluoropyrimidine Discontinuation

Except where specified below, both medications in the oxaliplatin-plus-fluoropyrimidine chemotherapy regimen should be discontinued for any of the following reasons:

- Any Grade ≥ 4 peripheral neuropathy requires discontinuation of oxaliplatin.
- In case of persistent Grade 3 paraesthesia, oxaliplatin should be discontinued.
- Any Grade ≥ 3 mucocutaneous reaction possibly attributable to capecitabine, leucovorin, or tegafur-gimeracil-oteracil requires permanent discontinuation.
- Grade ≥ 3 drug-related thrombocytopenia associated with clinically significant bleeding.
- Any drug-related liver function test abnormality that meets the following criteria requires discontinuation:
 - AST or ALT > 5 to 10 × ULN for > 2 weeks
 - AST or ALT > 10 × ULN
 - Total bilirubin > 5 × ULN
 - Concurrent aspartate aminotransferase (AST) or alanine aminotransferase (ALT) > 3 × ULN and total bilirubin > 2 × ULN

- Any oxaliplatin-related decrease in creatinine clearance to < 30 mL/min (using the Cockcroft Gault formula) requires discontinuation of oxaliplatin.
- Any drug-related AE that recurs after 2 prior dose reductions for the same drug-related AE requires discontinuation of the drug(s) that was/were previously dose reduced.
- Any Grade ≥ 3 drug-related hypersensitivity reaction or infusion reaction requires discontinuation of the drug(s) felt to be causing the reaction. The drug not felt to be related to the hypersensitivity reaction or infusion reaction may be continued.
- Any Grade 4 drug-related AE that the investigator deems is inappropriate to be managed by dose reduction(s) requires discontinuation of the drug(s) felt to be causing the event. The drug not felt to be related to the event may be continued.
- If any toxicity does not resolve within 42 days, that component will be discontinued unless it is determined by the treating investigator that the participant might benefit from continuation of the component.

For toxicities that are not listed above, the treating investigators can decide to discontinue any individual chemotherapy agent, or all chemotherapy agents, if it is not the best interest in the participant per the local standards. If the fluoropyrimidine has to be discontinued completely, the benefit of continuing oxaliplatin should be carefully weighed against toxicity by the treating investigator per local standards.

Post-treatment study follow-up is critically important and is essential to preserving participant safety and the integrity of the study. Participants who discontinue study treatment will continue to be followed for collection of tumor surveillance assessments, safety [REDACTED] as per protocol.

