7.3.3.2 Dose Modification Criteria for XELOX

Capecitabine

Toxicity due to capecitabine administration may be managed by symptomatic treatment and/or treatment interruption or dose reduction. Dose modifications of capecitabine are presented in Table 7.3.3.2-1. Once the dose has been reduced, it should not be increased at a later time. For those toxicities considered by the treating physician to be unlikely to become serious or life threatening (eg, alopecia, altered taste, or nail changes), treatment can be continued at the same dose without reduction or interruption. Participants taking capecitabine should be informed of the need to interrupt treatment immediately if moderate or severe toxicity occurs. Doses of capecitabine omitted for toxicity are not replaced.

Table 7.3.3.2-1: Recommended Dose Modifications of Capecitabine

Toxicity ^a	During a Course of Therapy	Dose Adjustment for Next Treatments (% of starting dose)
Grade 1	Maintain dose level	Maintain dose level
Grade 2		
1st appearance	Interrupt until resolved to Grade 0 to 1	100% (1000 mg/m ²)
2nd appearance		75% (750 mg/m ²)
3rd appearance		50% (500 mg/m ²)
4th appearance	Discontinue treatment permanently	-
Grade 3		
1st appearance	Interrupt until resolved to Grade 0 to 1	75% (750 mg/m ²)
2nd appearance		50% (500 mg/m ²)
3rd appearance	Discontinue treatment permanently	-
Grade 4		
1st appearance	Discontinue treatment permanently or, if physician deems it to be in the participant's best interest to continue, interrupt until resolved to Grade 0 to 1	50% (500 mg/m ²)

^a According to the National Cancer Institute of Canada Clinical Trial Group (NCIC CTG) Common Toxicity Criteria (version 1) or the Common Terminology Criteria for Adverse Events (CTCAE) of the Cancer Therapy Evaluation Program, US National Cancer Institute, version 4.0.

Oxaliplatin

Dose Modifications for Neurotoxicity

- For Grade 2 peripheral sensory neuropathy (moderate paresthesia or dysesthesia), or limiting instrumental activities of daily living, skip oxaliplatin. When toxicity resolves to \leq Grade 1, resume oxaliplatin at 75% of initial dose. If oxaliplatin is skipped for 4 weeks (2 consecutive doses) for neurologic toxicity, discontinue oxaliplatin.
- For Grade 3 or greater peripheral sensory neuropathy (severe paresthesia or dysesthesia), or limiting self-care activities of daily living, discontinue oxaliplatin.

Dose Modifications for Participants with Renal Impairment

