8 DISCONTINUATION CRITERIA

8.1 Discontinuation from Study Treatment

Participants MUST discontinue IP (and non-IP at the discretion of the investigator) for any of the following reasons:

- Participant's request to stop study treatment. Participants who request to discontinue study treatment will remain in the study and must continue to be followed for protocol-specified follow-up procedures. The only exception to this is when a participant specifically withdraws consent for any further contact with him/her or persons previously authorized by participant to provide this information
- Any clinical AE, laboratory abnormality, or intercurrent illness that, in the opinion of the investigator, indicates that continued participation in the study is not in the best interest of the participant
- Termination of the study by BMS
- Loss of ability to freely provide consent through imprisonment or involuntarily incarceration for treatment of either a psychiatric or physical (eg, infectious disease) illness. (Note: Under specific circumstances, a participant who has been imprisoned may be permitted to continue as a participant. Strict conditions apply and BMS approval is required.)
- Documented radiographic PD per RECIST criteria, unless the participant meets criteria for treatment beyond progression
- Criteria listed in [Sections 7.3.3.2, 7.3.3.3, 7.3.3.4, 7.3.4, and 7.3.7](#)

Discontinuation of the study treatment for abnormal liver tests should be considered by the investigator when a participant meets 1 of the conditions outlined in [Section 9.2.7](#) or if the investigator believes that it is in the best interest of the participant.

Refer to the Schedule of Activities ([Section 2](#)) for data to be collected at the time of treatment discontinuation and follow-up and for any further evaluations that can be completed.

In the case of pregnancy, the investigator must immediately, within 24 hours of awareness of the pregnancy, notify the BMS Medical Monitor/designee of this event. In most cases, the study treatment will be permanently discontinued in an appropriate manner (eg, dose tapering if necessary for participant safety). Refer to [Section 9.2.5](#), Pregnancy.

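### Section 7.3.4 permanently stops treatment for Grade 3 or higher mucocutaneous reactions, an undefined term that as written covers stomatitis and hand-foot syndrome, which the SOX table manages by dose reduction with treatment continued

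*Protocol*

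**What the plan says.** Section 7.3.4 of the protocol lists reasons to stop chemotherapy. It opens: "Except where specified below, both medications in the oxaliplatin-plus-fluoropyrimidine chemotherapy regimen should be discontinued for any of the following reasons". One bullet says that any Grade 3 or higher "mucocutaneous reaction possibly attributable to capecitabine, leucovorin, or tegafur-gimeracil-oteracil requires permanent discontinuation". Investigator discretion comes only at the end, for events off the list: "For toxicities that are not listed above, the treating investigators can decide to discontinue any individual chemotherapy agent". The section's last sentence then asks the investigator to weigh the benefit of keeping oxaliplatin against its toxicity when the fluoropyrimidine has been stopped completely.

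Section 7.3.3.4 governs SOX. Table 7.3.3.4-3 has a row for "Diarrhea, stomatitis, Hand-Foot syndrome" at Grade 3 or higher, with a one-level reduction for oxaliplatin and for S-1. The text above the table says that "1 or both agents must be reduced according to Table 7.3.3.4-4 and be continued". Table 7.3.3.4-2 interrupts S-1 for the same events from Grade 2 and then resumes it. Footnote a of Table 7.3.3.4-4 says oxaliplatin should stop if S-1 stops.

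Section 7.3.3.2 governs capecitabine: "Toxicity due to capecitabine administration may be managed by symptomatic treatment and/or treatment interruption or dose reduction". Table 7.3.3.2-1, headed as recommended, is organised by grade and not by event. For a first or second Grade 3 toxicity it says "Interrupt until resolved to Grade 0 to 1", with the next dose at 75% and then 50%. It stops the drug at the third. A first Grade 4 toxicity may also resume at 50% if the physician judges that to be in the participant's interest.

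Section 8.1 states: "Participants MUST discontinue IP (and non-IP at the discretion of the investigator) for any of the following reasons". Its list cites Sections 7.3.3.2, 7.3.3.3, 7.3.3.4, 7.3.4 and 7.3.7 in a single line, without ranking them.

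**The concern.** Stomatitis is a mucosal event and hand-foot syndrome is a skin event. Unless the protocol says otherwise, a site would class either as a mucocutaneous reaction. A participant on SOX with a first Grade 3 episode then falls under a rule that ends treatment for good and under another that reduces the dose and carries on. The outcome depends on which section the site opens.

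Two things are at stake. One is how much chemotherapy the participant receives after the event. The other is reporting: adverse events leading to discontinuation are part of a stated secondary safety endpoint (Protocol Table 4-1). The SAP assigns events by the recorded action (Section 7.1.1) and tabulates discontinuations (7.6.3) separately from delays and reductions (7.6.4). Two identical events could land in different tables because two sites read different pages.

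**Working it through.** The plan states no figure on this point to reproduce, so the check is a comparison of rules, with arithmetic only for the dose consequence.

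**Do the two SOX rules address the same case?**

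| | Section 7.3.4 bullet | Table 7.3.3.4-3 row |
|---|---|---|
| Event | Mucocutaneous reaction, undefined | Stomatitis and hand-foot syndrome, named |
| Grade | 3 or higher | 3 or higher |
| Drug | S-1 named, also capecitabine and leucovorin | S-1 and oxaliplatin |
| Force | Requires | Must |
| Action | Permanent stop | One level down, continue |

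Grade, drug and force match, and the actions are opposite. Only the event column needs a reading. The bullet applies to any such reaction that is possibly attributable, so it carries no narrowing language. Diarrhea sits in the same SOX row but is not mucocutaneous, so it is not part of the conflict.

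**Does another section settle it?**
- Section 8.1 cites both sections and does not rank them.
- Section 7.3.1 sends events attributed to chemotherapy alone to Sections 7.3.3.2 to 7.3.3.4 and does not mention 7.3.4. A site following that route reaches the reduction tables first.
- The instruction in Section 7.3.1 to follow the most conservative guideline covers events possibly related to the combination of immunotherapy and chemotherapy. It does not reach an event attributed to chemotherapy alone.
- Section 7.3.3 permits modification by local standard or package insert, but it does not waive a rule that requires permanent discontinuation.
- The discretion in Section 7.3.4 is for unlisted toxicities, and this one is listed.

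**Dose after a first Grade 3 event, as a share of the starting dose (Tables 7.3.3.4-4 and 7.3.3.2-1).**
- S-1, one level down: 25/40 = 63%, 40/50 = 80% and 50/60 = 83% for the three body-surface bands. Under 7.3.4: 0%.
- Oxaliplatin in SOX, one level down: 100/130 = 77%. Under 7.3.4: see the next item.
- Capecitabine, first Grade 3: 750/1000 = 75%. Under 7.3.4: 0%.

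**One drug or both?** The bullet does not name the drug to be stopped. Neighbouring bullets do: neuropathy stops oxaliplatin, and hypersensitivity stops the drug thought responsible. By the lead sentence, silence means both drugs stop. The closing sentence of the section treats continuing oxaliplatin as something to weigh. For SOX, footnote a of Table 7.3.3.4-4 stops oxaliplatin with S-1; XELOX has no such footnote. The fate of oxaliplatin is therefore unsettled within Section 7.3.4, and the footnote adds a further rule for SOX only.

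**The case against.** The best defence is that the bullet was meant for severe skin and mucosal syndromes. The protocol writes stomatitis and hand-foot syndrome when it means them, and Section 7.3.4 uses a different term. The bullet also names leucovorin but not fluorouracil, which is odd for a rule about ordinary fluoropyrimidine toxicity. This is a fair account of possible intent, but the text does not say it. The skin algorithm in Appendix 8 names Stevens-Johnson syndrome and toxic epidermal necrolysis (as SJS and TEN) where it means them. If the narrow meaning was intended, stating it is the remedy.

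A second defence is that the Section 8.1 list is disjunctive: one criterion is enough, and a dose-reduction row cannot cancel it. Read alone, 8.1 does lean that way. It still leaves in place a SOX instruction that both agents must be reduced and continued.

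The defence carries more weight for capecitabine. Table 7.3.3.2-1 is a recommended, generic ladder that names no skin or mucosal event, so the bullet can be read as an exception to it. A reader might infer a second direct contradiction here. The text supports only an overlap with no stated carve-out.

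A reader might also infer that oxaliplatin is lost automatically. The closing sentence of Section 7.3.4 prevents that conclusion for XELOX.

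**Conclusion.** The conflict is real and is direct for SOX. At Grade 3 or higher, stomatitis and hand-foot syndrome fall under a permanent stop and under a mandatory reduction with continuation. For S-1 the difference is 0% against 63% to 83% of the starting dose. This rests on one reading: that an undefined term, applied to any such reaction, covers an oral mucosal event and a skin event. The capecitabine overlap is softer, and whether one drug or both stop is left open.

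Two larger conclusions might be drawn, and neither is supported. One is a count of participants affected. The documents give neither the incidence of these events nor the share of participants on each regimen, and only SOX names the events, so any count would be built on assumptions and would blur the direct conflict with the soft one. The other is bias in the primary response-rate comparison, through earlier subsequent therapy that shortens the best-response window. Section 5.1.2 lets BMS-986213 or nivolumab continue alone after chemotherapy is stopped for toxicity, both arms share the same chemotherapy rules, and nothing in the documents shows a difference between arms. What is supported is inconsistent management and inconsistent counting of the same event across sites.

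**What to change.** Reconcile the mucocutaneous bullet in Section 7.3.4 with Table 7.3.3.4-3, footnote a of Table 7.3.3.4-4 and Table 7.3.3.2-1. The revised text should state:
- which reactions the bullet covers;
- whether stomatitis and hand-foot syndrome are inside or outside it;
- whether one drug or both stop, for each regimen, in agreement with the lead and closing sentences of Section 7.3.4;
- which section prevails when both apply.

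Which action is right is a clinical decision for the sponsor's team, and this point takes no position on it.

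The cost is one reworded bullet and cross-references in the tables, by amendment or administrative letter, with no added procedures or data. The SAP needs no change. The by-subject listings already planned in SAP Sections 7.6.3 and 7.6.4 would show how events before the change were handled.

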7.3 Dosage Modification

7.3.1 Dose Modification Criteria for BMS-986213 or Nivolumab Plus Chemotherapy

If AEs are considered to be related to study treatment (BMS-986213 or nivolumab OR chemotherapy), every attempt must be made to attribute the individual study treatment to the AE, if possible, or to the combination regimen.

- For AEs that are deemed to be related to BMS-986213 or nivolumab ONLY by the treating physician, dose delays are permitted (see [Section 7.3.5](#)). Dose reductions are not permitted (see [Section 7.3.2](#)). The chemotherapy should continue as scheduled.
- For AEs that are deemed to be related to the chemotherapy ONLY by the treating physician, dose modifications are permitted according to local standard or local package insert (see [Sections 7.3.3.2](#) for XELOX, [7.3.3.3](#) for FOLFOX, and [7.3.3.4](#) for SOX). BMS-986213 or nivolumab administration should continue as scheduled.
- For AEs that are possibly related to the combination regimen (BMS-986213 or nivolumab PLUS chemotherapy), the most conservative toxicity management guidelines must be followed.
- If there is a delay in administration of study drug(s) due to toxicity, treatment with the other study agent(s) should continue as scheduled. Resumption of treatment should be at the next scheduled time point if criteria to resume treatment are met.

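### In SOX, a third occurrence of the same oxaliplatin-only toxicity is to be reduced and continued under Protocol 7.3.3.4 but discontinued under Protocol 7.3.4

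*Protocol*

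**What the plan says.** Protocol Section 7.3.3.4 lists events (Table 7.3.3.4-3) that trigger a lower SOX dose. The text introducing that table says that if any of them is met, "1 or both agents must be reduced according to Table 7.3.3.4-4 and be continued". It makes no exception for repeat occurrences and does not cite Section 7.3.4.

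Table 7.3.3.4-4 holds the dose ladder. Oxaliplatin starts at 130 mg/m² and falls to 100, then 75, then 50 at the row labelled "3-level reduction". It stops at the row labelled "4-level reduction". S-1 has two reduced doses and is discontinued at its third step, where a footnote adds: "If tegafur-gimeracil-oteracil potassium combination drug is discontinued, oxaliplatin should also be discontinued".

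Section 7.3.4 applies to all oxaliplatin-plus-fluoropyrimidine regimens. One bullet reads "Any drug-related AE that recurs after 2 prior dose reductions for the same drug-related AE requires discontinuation of the drug(s" …, and the rest of the sentence limits this to drugs already reduced. It contains no SOX exception.

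Two other passages bear on precedence. Section 8.1 lists reasons for which treatment must stop, among them the criteria in "Sections 7.3.3.2, 7.3.3.3, 7.3.3.4, 7.3.4, and 7.3.7". Section 7.3.1 says that for events possibly related to immunotherapy plus chemotherapy "the most conservative toxicity management guidelines must be followed". Events attributed to chemotherapy only are sent to the regimen-specific sections, which for SOX means 7.3.3.4.

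**The concern.** Both instructions are written as mandatory, and for one class of event they cannot both be followed. A site working from the SOX tables would lower oxaliplatin and carry on. A site working from the general discontinuation list would stop it.

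This is first a question of consistent participant management. It also reaches the analysis. SAP Section 7.1.1 classifies adverse events by the recorded action on study drug. The same clinical course would therefore be counted under discontinuation (SAP 7.6.3) at one site and under dose modification (SAP 7.6.4) at another, assuming the action is recorded for oxaliplatin as a study drug. The incidence of adverse events leading to discontinuation is a stated secondary safety endpoint. Oxaliplatin dose intensity (SAP Table 7.4.1-3) would also differ.

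**Working it through.** The plan gives no figure to reproduce. The check steps each Table 7.3.3.4-3 criterion that calls for a one-level reduction through the Table 7.3.3.4-4 ladder, for repeated occurrences of the same event, and compares each step with the 7.3.4 bullet.

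**Inputs**
- Oxaliplatin ladder (Table 7.3.3.4-4): 130, 100, 75, 50 mg/m², then discontinued.
- S-1 ladder (same table, BSA of 1.5 m² or more as the example): 60, 50, 40 mg/dose, then discontinued. The footnote then stops oxaliplatin.
- Criteria that lower oxaliplatin only (Table 7.3.3.4-3): platelets below threshold and not recovered within 7 days of the planned date; Grade 2 peripheral neuropathy. The oxaliplatin cell of the 75,000/mm³ platelet row is blank in the extracted text. I read it as merged with the one-level reduction in the row above.
- Criteria that lower both drugs: Grade 4 platelets; Grade 4 neutrophils; febrile neutropenia; Grade 3 or higher diarrhea, stomatitis or hand-foot syndrome.

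**Side by side, same event repeated**

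| Occurrence | 7.3.3.4, oxaliplatin-only criterion | 7.3.3.4, criterion lowering both drugs | 7.3.4 bullet |
|---|---|---|---|
| 1 | oxaliplatin 100, S-1 60 | oxaliplatin 100, S-1 50 | not triggered |
| 2 | oxaliplatin 75, S-1 60 | oxaliplatin 75, S-1 40 | not triggered |
| 3 | oxaliplatin 50, continue | S-1 discontinued, so oxaliplatin stops | stop the reduced drug(s) |

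At the third occurrence the second column conflicts with 7.3.4 and the third column agrees with it.

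**Different events.** The 7.3.4 bullet counts only prior reductions for the same event. A participant who reaches 50 mg/m² through, say, a platelet reduction and then neuropathy has not triggered it, so there is no conflict.

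**Fourth platelet event.** Table 7.3.3.4-3 has a platelet row marked "only for dose of 50 mg/m"² that leaves oxaliplatin unchanged and lowers S-1. For someone who reached 50 mg/m² through repeated low platelets, oxaliplatin would still be running one event after 7.3.4 required it to stop.

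**Illustration for dose intensity.** SAP Table 7.4.1-3 divides the cumulative oxaliplatin dose by (last dose date − first dose date + 21) × 130/21. Assume one dose at each level, 21 days apart.
- Stop at the third occurrence: (130 + 100 + 75) / [(42 + 21) × 130/21] = 305/390 = 78%.
- Continue with one dose at 50: (130 + 100 + 75 + 50) / [(63 + 21) × 130/21] = 355/520 = 68%.

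These fall in different categories of SAP Section 7.4.1 (70 to <90% and 50 to <70%). Equal numbers of doses at each level give the same percentages. Extra doses at the full 130 add equally to numerator and denominator, so they raise both percentages and narrow the gap, and the category need not change.

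**The case against.** The strongest reply is that Section 8.1 already settles the matter. It is a list of alternative reasons to stop, so meeting any one suffices, and 7.3.4 is on it. The instruction to continue also cannot be absolute, because the tables it relies on contain their own entries for skipping and discontinuing. Section 7.3.3 allows modification by local standards, and 7.3.1 has its conservative rule. On this view only a cross-reference is missing.

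Part of this stands. Section 8.1 does make the 7.3.4 stop binding, and a careful reader could resolve the conflict that way. But 8.1 does not qualify the sentence in 7.3.3.4 that the dose must be lowered and continued. The skip and discontinue entries in Table 7.3.3.4-3 are for named rows (Grade 3 or higher oxaliplatin hypersensitivity, Grade 3 and Grade 4 neuropathy), not for a third low platelet count or a third Grade 2 neuropathy. The 7.3.1 rule does not cover an event attributed to chemotherapy only. Permission to follow local standards does not reconcile one passage saying the drug must be continued with another requiring it to stop.

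Several stronger readings are tempting and not supported:
- A reader might infer that every third occurrence in SOX is affected. The footnote on S-1 rules that out for criteria lowering both drugs.
- A reader might infer that a third oxaliplatin level contradicts 7.3.4 by itself, or that the platelet row at 50 mg/m² shows three reductions for one event were intended. Both have a consistent use when the reductions were for different events.
- A reader might infer that Section 8.1 makes both passages mandatory, or that 7.3.3.4 overrides 7.3.4. Section 8.1 mandates stop criteria only, and nothing in 7.3.3.4 claims precedence.

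**Conclusion.** A real but narrow internal contradiction. In SOX, for platelet criteria below Grade 4 and for Grade 2 peripheral neuropathy, a third occurrence of the same event leads to 50 mg/m² and continuation under 7.3.3.4, and to discontinuation of oxaliplatin under 7.3.4.

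One dose step is at issue, in participants who meet the same oxaliplatin-only criterion three times. The documents do not state how many participants receive SOX, so the number affected cannot be given and may be small. Sample size, alpha and power are unaffected, and the material gives no ground for claiming an effect on the response-rate comparison. A reader might infer a difference between arms because the trial is open-label. That is possible, but no figure in the documents supports it.

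The conclusion assumes that the event is attributed to chemotherapy only. For the 75,000/mm³ platelet row it also rests on the merged-cell reading stated above. The neuropathy case does not depend on that reading.

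**What to change.** Reconcile the reduce-and-continue sentence of 7.3.3.4 and the Table 7.3.3.4-4 ladder with the two-reductions bullet of 7.3.4, by stating which governs a third occurrence of the same oxaliplatin-only event. This could be an exception for the SOX ladder in 7.3.4, or a note to the table saying that its third oxaliplatin level is not for recurrence of the same event. The sponsor's medical team decides which. I take no position on the clinical rule. The platelet row for participants already at 50 mg/m² should be checked against whichever wording is chosen.

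The cost is one sentence of protocol text and a cross-reference. No analysis method or sample size changes.
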